#### i.iii. Data imputations for key outcomes as sensitivity analyses

Further to the initial SAP outlined in section 4, multiple imputations by chained equation were used to impute missing data for several key outcomes (adherence to psychotropic medications, health state utility, and K6 total score) as part of the sensitivity analyses to explore the impact of missing data. Data imputations were implemented separately by randomised treatment groups with the assumption that data were missing at random (Faria, Gomes, Epstein, & White, 2014). Sixty iterations were performed on these imputations and data were analysed using the imputed dataset with results collated according to Rubin's rules, which would reflect the variability within and across imputations (White et al., 2011). A user-contributed Stata program package (ICE) was used to implement the multiple imputations, which is flexible to impute different types of data.

Variables included in the equations were slightly different for the three outcomes. For the adherence to psychotropic medications outcome, approximately 13% of missing data at follow-up were imputed using the multiple imputations by chained equations, with age, sex, number of self-reported mental illnesses, number of self-reported physical health conditions, service completion status and baseline self-reported adherence to medications (RAM) score included in the equations.

For the health state utility, variables included in the equations were age, sex, level of education, employment status, number of self-reported mental illnesses, number of self-reported physical health conditions, self-reported general health, death indicator, and the baseline utility scores. And for the K6 total score, variables included in the equations were age, sex, level of education, employment status, number of self-reported mental illnesses, number of self-reported physical health conditions, self-reported general health, and the baseline K6 scores.

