**Primary analysis:** A mixed-effects logistic regression model will be applied to compare the medication's adherence rate over the 6 months after initial intervention/comparator service between IG and CG. RCT group will be entered as fixed effect and pharmacy entered as a random intercept to account for possible non-independence of observations from participants who attend the same pharmacy. The baseline value of the outcome variable will be included as a covariable in the model. The effect estimate will be reported as an odds ratio with 95% confidence interval.

**Sensitivity analysis:** To assess the robustness of the results, sensitivity analysis will be performed for this primary outcome, using the linked PBS data sample.

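### The sensitivity imputation for objective adherence leaves out baseline objective adherence and pharmacy, both of which are in the analysis model

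*SAP*

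**What the plan says.** Section i.iii adds multiple imputation by chained equations, as a sensitivity analysis, for three outcomes: objective adherence to psychotropics, health state utility and the K6 total.

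- **Mechanism:** "Data imputations were implemented separately by randomised treatment groups with the assumption that data were missing at random".
- **Amount, adherence:** "approximately 13% of missing data at follow-up were imputed using the multiple imputations by chained equations". I read this as about 13% of participants lacking the follow-up value.
- **Predictors, adherence:** age, sex, number of mental illnesses, number of physical conditions, "service completion status and baseline self-reported adherence to medications (RAM) score included in the equations".
- **Predictors, utility:** the list ends with "self-reported general health, death indicator, and the baseline utility scores".
- **Predictors, K6:** the list ends with "self-reported general health, and the baseline K6 scores".

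Section 4.1.1 analyses objective adherence by mixed-effects logistic regression. On baseline it says: "The baseline value of the outcome variable will be included as a covariable in the model". On clustering it has "pharmacy entered as a random intercept to account for possible non-independence of observations from participants who attend the same pharmacy". Section 4.2 gives the same random intercept to the secondary outcomes.

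**The concern.** An imputation model should contain at least the variables and structure of the model that will analyse the imputed data. Otherwise the imputed values follow a relationship that the analysis model contradicts. Two terms are absent here.

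**Baseline objective adherence.** Within each arm, imputed outcomes are unrelated to baseline dispensing-based adherence except through the listed predictors. Baseline RAM is a partial proxy only: section 4.1 defines it as self-report on all prescribed medications, whereas the outcome is dispensing-based and limited to psychotropics. The other two equations include their own baselines, so adherence is the exception.

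**Pharmacy.** Imputed values carry no within-pharmacy correlation, although every comparative model assumes some.

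If missingness depends only on arm and baseline adherence, the baseline-adjusted complete-case model is already consistent for the treatment effect. The imputation could then introduce a shift that the primary analysis did not have, and the comparison of the two results would falsely alarm or falsely reassure.

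**Working it through.** **1. Model terms side by side**

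| Term | Adherence imputation (i.iii) | Adherence analysis (4.1.1) |
|---|---|---|
| Arm | yes, imputed separately by arm | fixed effect |
| Baseline objective adherence | not listed | covariate |
| Baseline RAM | listed | not in model |
| Pharmacy | not listed | random intercept |

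**2. Effect of omitting baseline on the treatment odds ratio**

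The 13% is from the SAP. The rest is assumed, because the SAP gives no data on it: 60% adherent at baseline; control log-odds −0.8 for baseline non-adherers; baseline-outcome OR of 3, 6 or 10; true treatment OR of 1.0, 1.5 or 2.0. RAM and the other predictors are given no explanatory power, so this is a worst case.

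Let P(t,b) be the true adherence probability in arm t at baseline status b, and m(t,b) the fraction missing. Imputation that ignores b draws from the observed arm rate

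I(t) = Σ_b w_b(1−m)P / Σ_b w_b(1−m),

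so the completed data have probability Q(t,b) = (1−m)P + m·I(t). The adjusted logistic model is then fitted to Q.

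Worked case: no true effect, baseline OR 6, so P = 0.310 (b=0) and 0.729 (b=1) in both arms. Missingness is 28% (b=0) and 3% (b=1) in the intervention group, and 13% throughout in the comparator group. The intervention total is 0.4×0.28 + 0.6×0.03 = 0.13.

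- I(intervention) = (0.4×0.72×0.310 + 0.6×0.97×0.729)/0.87 = 0.591
- I(comparator) = 0.4×0.310 + 0.6×0.729 = 0.562
- Q, b=0: 0.389 v 0.343, OR 1.22
- Q, b=1: 0.725 v 0.708, OR 1.09
- Common adjusted OR: 1.14, when the truth is 1.00

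All cases (range over baseline OR 3 to 10):

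| Missingness pattern | True 1.0 | True 1.5 | True 2.0 |
|---|---|---|---|
| Completely random, 13% | 1.00 | 1.45-1.49 | 1.90-1.98 |
| By baseline, same in both arms (22% / 7%) | 1.00 | 1.45-1.49 | 1.89-1.97 |
| By baseline in intervention arm only (28% / 3%) | 1.08-1.20 | 1.61-1.75 | 2.14-2.28 |
| Opposite in the two arms (28% / 3% v 3% / 19.7%) | 1.14-1.36 | 1.70-1.98 | 2.25-2.59 |

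Reversing the arms would reverse the direction. With baseline objective adherence in the equations, the limit equals the true OR in every row.

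A simulation under milder assumptions agrees: 300 trials, 50 pharmacies of 8, intervention losses 24% v 4% by baseline, baseline log-odds effect 1.7, no true effect. Mean log OR was 0.013 with full data, 0.112 imputed without baseline and 0.011 imputed with it. The shift of 0.112 − 0.013 = 0.099 is an OR of about 1.10.

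**3. Effect of omitting pharmacy on the standard error**

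A pair of participants in one pharmacy keeps its correlation only if both are observed, so the ICC shrinks by about 0.87² = 0.757. The SE ratio is √{[1+(m−1)·0.757·ICC] / [1+(m−1)·ICC]}, where m is now participants per pharmacy. Both m and the ICC are assumed.

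| m | ICC 0.02 | ICC 0.05 | ICC 0.10 |
|---|---|---|---|
| 5 | 0.991 | 0.980 | 0.965 |
| 8 | 0.985 | 0.968 | 0.949 |
| 12 | 0.978 | 0.956 | 0.934 |

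Standard errors are therefore about 1% to 7% too small. The 13% applies to adherence; the SAP gives no missing fraction for utility or K6.

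**The case against.** **Baseline may be missing for the same people.** Both time points come from PBS and dispensing records, so someone unlinked may lack both. RAM may then be their only baseline adherence measure, and adding the dispensing baseline would gain little for them. This stands as a limit on the benefit. It does not rescue the present list: section i.iii does not name baseline objective adherence among the imputed variables, and a participant without it would drop out of the adjusted model even after the follow-up value was imputed.

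**The shift needs arm-differential missingness, which nothing in the SAP shows.** Correct. Imputing by arm keeps a null at 1.00 in the non-differential rows, and RAM would reduce the shift by an unknown amount. A reader might infer that the check is itself biased; the SAP supports only that it can be.

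**The clustering effect is small.** Also correct. The approximation further leaves out the between-imputation variance that Rubin's rules add.

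**Deaths.** A reader might infer from the death indicator in the utility equation that participants who died were given survivors' utilities. The SAP does not say so. The indicator could equally serve to separate participants to whom a fixed value had already been assigned. Health state utility is also not a tabulated outcome in section 4, where AQoL-6D appears as a 20-99 score. What remains is that the rule is not stated for utility or for K6.

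**Conclusion.** The incompatibility holds on the SAP's own text: two terms of the adherence analysis model are missing from its imputation model, and pharmacy is missing from all three. The baseline omission matters more.

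Its size rests on assumed inputs. It ranges from no shift of a null, with mild attenuation of real effects (2.0 to 1.89-1.98), when missingness does not differ by arm, to a null OR of about 1.1 under moderate arm-differential missingness, and higher in the extreme pattern. The SAP has no data to say which applies. The pharmacy omission costs about 1-7% in the standard error.

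This is a sensitivity analysis, so neither co-primary estimate changes. It is, however, the SAP's only imputation-based check on a co-primary outcome that section 1.1 says will inform MSAC applications, so it should be corrected. The handling of deaths is unclear rather than shown to be wrong.

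**What to change.** - **Adherence equations:** add baseline objective adherence. Where it is itself missing, impute it jointly with the follow-up value and keep baseline RAM as an auxiliary variable. Report how many participants lack each value, by arm.
- **All three imputations:** carry pharmacy, by multilevel imputation or by pharmacy indicators where cluster size allows. Region and mean baseline MPR are optional, since neither is in the analysis model.
- **Deaths:** state whether utility and K6 after death are imputed. If a fixed post-death utility is assigned, keep those participants out of the model fitted to survivors, so that their values do not pull down survivors' imputed utilities. Assigning the value and simply dropping the indicator would not achieve this.

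The cost is new wording, some extra modelling work (multilevel imputation in particular) and a re-run on data already held. Section i.iii is written in the past tense, so the re-run should be reported as a revised sensitivity analysis alongside the existing one.

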## 2. Analysis principles

**General analysis:** Comparative analyses will allow for the clustered nature of the data and baseline values will be adjusted in the models. The cluster will be the community pharmacy and the analysing unit will be the individual consumer participant.

**Stratified analysis:** Stratified analyses will be conducted based on the metropolitan or non-metropolitan location of community pharmacies.

**Intention-to-treat analysis:** All analyses will be undertaken based on the 'intention-to-treat' principle, that is, participants' data will be analysed according to the group to which they were initially allocated (White et al., 2011).

**Per-protocol analysis:** Due to the impact of the novel coronavirus (COVID-19) pandemic, consumer participants may have not completed each data collection milestone within the targeted timeframe. For example, a 6-month review including a follow-up survey should be completed 6 months after the initial intervention/comparator service interview with the participating pharmacist. However, some consumer participants were unable to attend appointments as scheduled due to state-wide lockdowns and other factors associated with the pandemic such as social distancing. A per-protocol sample is defined if consumer participants who have completed the initial pharmacist intervention/comparator service interview within 8 weeks after completing the baseline survey, and if they have completed the 6-month follow-up survey within 16-32 weeks after the initial pharmacist intervention/comparator service interview. Participants, who have received extra medication management services, such as a home medicines review (HMR), will be excluded from the perprotocol analysis to eliminate potential contaminations between groups. Per-protocol analyses will be undertaken for the co-primary outcomes (subjective and objective measures of adherence) and several key secondary outcomes.

**Exclusions**: Data will be excluded if participants actively withdraw and request that their data are destroyed.

**Presentation of results**: Descriptive data will be summarised as mean (SD) or median (range or 25-75th percentile) for continuous variables and frequency (percentage) for categorical variables, respectively. Between-group comparisons will be calculated and presented with 95% confidence intervals wherever possible.

**Level of significance**: The statistical significance level will be set at less than 5%.

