#### 3.1 Data sources and analysis samples

The data will be collected from a number of sources depending on the type of information collected and the availability of the data. There are six samples used in this analysis plan, which are defined below:

**Baseline completion data sample**: Consumer participants who consented to participate in the study and completed a baseline process, which included a baseline survey and an initial interview with the pharmacist, will be considered members of the baseline completion data sample.

**Survey completion data sample:** Consenting participants will be assessed at baseline and reassessed at the 6-month endpoint using online questionnaires. Consumer participants will be considered members of the survey completion data sample if they completed surveys at both the baseline and 6-month points.

**Service completion data sample:** Consumer participants allocated in different arms will receive relevant intervention and comparator services. Clinical implementation outcomes relating to these services will be recorded by participating pharmacists using a purpose-designed research module developed by Guild Link. Consumer participants will be considered members of the service completion data sample if they have completed at least the initial pharmacist interview for an intervention or comparator service.

Linked hospital data sample: All consented consumer participants' hospital admission and emergency department visit data in the relevant jurisdiction will be linked based on a participant's identifiers, including name, date of birth, sex, and current residence. Consumer participants who have completed the baseline process, and whose hospital data were provided by the relevant data linkage agencies will be considered members of the linked hospital data sample.

Linked MBS/PBS data sample: All consumer participants with a valid consent form for MBS and PBS data linkage will be linked for health care (MBS) and pharmaceutical utilisation (PBS) data through Service Australia. Consumer participants successfully linked to the MBS and PBS database will be considered members of the linked MBS/PBS data sample.

**Pharmacy dispensing history data sample:** Consumer participants with dispensing history records provided by Guild Care or participating pharmacies will be considered members of the pharmacy dispensing history data sample.

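### The K6 imputation uses baseline variables only, and the utility imputation adds only a death indicator, so this sensitivity analysis can say little about missingness tied to events after baseline

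*SAP*

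**What the plan says.** Section i.iii adds multiple imputation by chained equations for three outcomes, as a sensitivity analysis of the effect of missing data. The stated assumption is: "Data imputations were implemented separately by randomised treatment groups with the assumption that data were missing at random".

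The three variable lists differ:

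- **K6 total score:** "And for the K6 total score, variables included in the equations were age, sex, level of education, employment status, number of self-reported mental illnesses". The list goes on with a count of physical conditions, general health and baseline K6. Table 3.2 places general health among the baseline characteristics, so none of the eight variables is post-baseline.
- **Health state utility:** the same seven non-outcome variables, ending with "self-reported general health, death indicator, and the baseline utility scores". The death indicator is the only post-baseline variable.
- **Psychotropic adherence:** age, sex, the two condition counts, "service completion status and baseline self-reported adherence to medications (RAM) score included in the equations". Service completion status is post-randomisation.

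The main survey analyses (sections 3.1 and 4.2.3) use participants who completed both surveys. Section 4.2 adjusts for the baseline value of the outcome where possible.

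Section 2 places the survey inside a service contact: "a 6-month review including a follow-up survey should be completed 6 months after the initial intervention/comparator service interview". Section 3.1 says of hospital data: "All consented consumer participants' hospital admission and emergency department visit data in the relevant jurisdiction will be linked". Membership of that sample needs the baseline process and data from the linkage agency. Membership of the service sample needs only the initial interview. Neither requires the 6-month survey.

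**The concern.** A sensitivity analysis for missing data is informative when it uses something the main analysis did not. Here both analyses assume in effect that, given baseline, people who did not return the survey resemble those in their arm who did. Agreement between the two is then close to built in, and it says little about missingness related to what happened after the service began.

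The trial can hold such information on non-returners: how far they went through the service, and whether they were admitted or visited an ED. The plan uses service completion status for dispensing-based adherence, an outcome that does not come from the survey. It leaves that status out for K6 and utility, which do come from the survey, and gives no reason.

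At stake is the reading of a secondary outcome. If K6 completers are a selected group and the selection differs by arm, a matching imputed result could be taken as more support than it gives.

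**Working it through.** **1. Can a plan figure be reproduced?** No. The SAP gives no sample size, K6 SD or survey missing rate. Its only missing rate, about 13%, is for psychotropic adherence. Every size below therefore rests on assumed inputs.

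**2. Post-baseline variables per equation (section i.iii).** K6: 0 of 8. Utility: 1 of 9 (death indicator). Adherence: 1 of 6 (service completion status).

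**3. Where a shared bias would come from.** Let *E* be a post-service event with effect γ on the outcome, given baseline. Let π be its prevalence in an arm and π_obs its prevalence among that arm's responders. Completer analysis and baseline-only imputation both put π_obs where π belongs, so approximately

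bias in the difference = γ × [(π_obs − π) in IG − (π_obs − π) in CG].

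This is zero if *E* does not affect non-return, or if the shift is equal in both arms.

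Hand example with assumed inputs:
- π = 0.25 in both arms, rounded from the statement in section i.ii that almost three quarters had no hospital or ED record
- γ = 0.6 SD
- overall missing 13%
- log-odds of missingness raised by the event by 1.0 in CG and 2.0 in IG

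Solving for 13% overall gives missing probabilities of 0.078 without the event, and 0.187 (CG) and 0.385 (IG) with it.

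- CG: π_obs = 0.25×0.813 / (0.25×0.813 + 0.75×0.922) = 0.227, a shift of −0.023.
- IG: π_obs = 0.25×0.615 / (0.25×0.615 + 0.75×0.922) = 0.182, a shift of −0.068.
- Bias = 0.6 × (−0.068 + 0.023) = −0.027 SD.

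**4. Simulation in SD units.** 360 participants, 600 runs per setting, no clustering, 10–30% missing, event effect 0.3–1.0 SD, and the same missingness model. The event was made somewhat less common in IG and related to baseline.

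| Setting | Full data | Completers | Baseline-only imputation | Event added |
|---|---|---|---|---|
| 13% missing, 0.6 SD, event drives missingness | −0.231 | −0.252 | −0.253 | −0.231 |
| 30% missing, 1.0 SD, event drives missingness | −0.262 | −0.311 | −0.313 | −0.259 |
| 13% missing, 0.6 SD, event unrelated to missingness | −0.238 | −0.235 | −0.235 | −0.235 |

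The first row gives a completer bias of −0.252 + 0.231 = −0.021 SD, of the same order as the hand figure. Across all settings where the event drove missingness, the shared bias was about 0.01–0.05 SD. Baseline-only imputation differed from the completer estimate by 0.003–0.010 SD on average, with correlation 0.992–0.999.

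**5. Simulation in K6 points.** Assumed 250 per arm, SD 6, slope on baseline 0.6, 20–25% missing, no clustering; 400 trials per scenario.

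| Scenario | Completers | Baseline-only imputation | Post-service variables added |
|---|---|---|---|
| Service non-completion 30–35% against 15%, non-completers 3–4 points worse | −0.19 to −0.35 | −0.20 to −0.35 | +0.01 to −0.03 |
| Mental-health contacts 10% against 20% | +0.22 | +0.23 | +0.04 |
| No arm difference in these factors | none | none | none |

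The largest bias is 0.35/6 = 0.058, about 0.06 SD. Against simulated SDs of the estimate of 0.44–0.51, it is 0.35/0.51 = 0.69 to 0.35/0.44 = 0.80 of a standard error. The direction depends on the scenario.

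**6. What the simulations show.** That baseline-only imputation tracks the completer analysis is a general result. That the added variables remove the bias is built in, because the simulations let those variables drive missingness. The exact pair of variables proposed below was not simulated.

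**The case against.** The strongest reply is that section i.iii misstates nothing. It declares a missing-at-random assumption, and the choice of auxiliary variables under it is largely judgement. Much of the rest also stands:

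- **Mechanism.** A reader might infer that surveys go missing because people leave the service or get worse. The SAP does not say so. Section 2 gives lockdowns and other pandemic factors as reasons for missed appointments, and nothing says that non-return differs by arm.
- **Utility.** A reader might infer that the utility equation is also baseline-only. It is not, because of the death indicator. Section 4 plans AQoL-6D on a 20–99 score and no utility analysis, so there is no utility main result in this document for the imputation to repeat. For utility the point is only that surviving non-responders have no post-service information in the equation.
- **Tracking.** The K6 equation holds seven predictors besides baseline K6 and runs by arm. If those predictors strongly drive both missingness and outcome, the result could move. Close agreement is an expectation, not a certainty.
- **Auxiliaries.** Dispensing-based adherence is a poor candidate. Section 4.1.1 counts a drug only if it was dispensed at least twice both before and after the service, so for some participants it is undefined rather than missing. Mental-health contacts are a subset of hospital and ED contacts that are already uncommon (section i.ii).

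The reply does not remove the limitation. "Sixty iterations were performed on these imputations" reduces simulation noise, not dependence on the assumption. The per-protocol sample requires a completed follow-up survey, so it cannot inform on non-returners either.

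**Conclusion.** The point holds as a cheap improvement, not as an error. The K6 imputation has no post-baseline variable and the utility imputation has only death, while usable post-service records can exist for people without a follow-up survey. The K6 check will probably stay close to the completer result and cannot address missingness driven by later events.

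It would be tempting to conclude that the K6 result is biased or that the check will falsely reassure. The SAP does not support that. A shared bias needs post-service factors that affect both outcome and non-return, with a selection effect that differs by arm; none of this is documented. Its size is unknown. Under assumed inputs it was up to about 0.06 SD, below one standard error, and it concerns a sensitivity analysis of a secondary outcome.

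**What to change.** In section i.iii, within arm:

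1. Add service completion status to the K6 and utility equations, as already done for adherence.
2. Add an indicator of any hospital admission or ED visit in the 6 months after the initial service, where linked data exist. Impute it in the chain where linkage is missing.
3. Do not add dispensing-based adherence.
4. Report the result beside the current imputation, labelled as an updated sensitivity analysis. Section i.iii describes the imputation as already run, so disclose that these variables were chosen afterwards.

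Define service completion status in the text. The section 3.1 sample needs only the initial interview, which everyone in the baseline completion sample has had; a status defined that way would carry almost no information. If it instead means completing the 6-month review, tabulate it against survey return by arm first. The equation can learn from it only if some non-completers returned the survey.

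The cost is a few lines of SAP text and one rerun. Intervals may widen slightly (simulated SD 0.51–0.59 against 0.44–0.51 with the fuller set of auxiliaries), and linkage will be incomplete. The main analysis is untouched.
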